10.3.3 Secondary outcome analysis

Participants will complete three questionnaires at start of baseline, at start of treatment, 6 months, 12 months, and 18 months into the treatment and at the end of follow up. These scales evaluate quality of life (ReQol), patient satisfaction (Dialogue), and suicidality (Columbia Scale). Data from these questionnaires will be compared between the treatment phases with nonparametric test for repeated measures (Friedman Test). To evaluate whether change over time of the individuals scores on the ReQol-10, Dialogue and Columbia Scale a Reliable Change Index will be used.

Data from the qualitative interviews will be analysed through thematic analysis.

10.4 Subgroup analyses

Not applicable

10.5 Adjusted analysis

Not applicable

10.6 Interim analysis and criteria for the premature termination of the trial

In the event that an SAE occurs which is linked to the intervention, the study will be stopped.

10.7 Participant population

Data of patients who agree to participate in the study will be used for data-analysis. If the patient wants to stop participating in the study the patient will be asked if we can use the collected data up to and including that point in time.

10.8 Procedure(s) to account for missing or spurious data

The primary outcome data will be gathered weekly before each participant's individual MBT session, either by the therapist or via phone if the participant is absent. The secondary outcome measures will be collected by the research assistant. Patients will be attending at least weekly sessions at the location, so the research assistant and therapists will have regular contact with the participants to remind them to fill out the questionnaires.

In case of missing data we will try to find the reason that the participant did not fill out the questionnaire. In case of random missing data the data analysis contain an implicit imputation. In case of drop-out we will try to describe the reason for drop-out, because we are interested whether this treatment is feasible for older patients with personality disorders.

10.9 Other statistical considerations.

In case of slow recruitment rate an amendment to this protocol will be submitted to request for extension the recruitment period of 3 years.

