7.1 Recruitment

Participants will come from a Later Life MBT service in Manchester, which exclusively serves older adults and offers a comprehensive MBT program. The study aims to collect data from 10 older adults for an 18-month treatment duration. As the population is likely to have multiple physical comorbidities, the study will aim to recruit 14 participants, with the expectation that there will be some attrition in the screening and introductory phases.

Single Case Experimental Design studies consider several factors for power, including participant count, observations, inter-participant correlation, and the likelihood of false positives (Shadish et al., 2014). To ensure adequate power, we'll collect weekly outcome data on personality functioning using the LPFS 2.0 and data on loneliness using the Social Isolation Short Form 4a before, during and after the 18 months treatment from the participants.

Participants will be sourced from an existing later life MBT service. All will have a confirmed personality disorder diagnosis based on the DSM-5 structured clinical interview (SCID-5-PD) or subthreshold. Those not meeting this criteria will not be excluded from the service if MBT is clinically indicated. When participants fulfil only one criterium under the cutoff point at the SCID5-PD interview, they will also be included in the study, but it will be clearly indicated that they are 'sub-threshold' to a full diagnosis of personality disorder.

Typically, referrals to the later life MBT service come from older adult community-based mental health teams in England, overseen by the NHS. All study participants will receive standard treatment, including regular meetings with a mental health professional and periodic reviews with a consultant psychiatrist. No restrictions will be placed on participants seeking other treatments, though concurrent psychological treatments might be contraindicated.

All participants will be aged 65 or older, with no upper age limit. The study won't control for other demographics, except that participants must reside in Manchester. Free transport can be arranged for participants, and in rare cases, treatment can be provided at home or in hospital wards due to frequent treatment disruptions from physical ailments or illnesses in older adults.

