10.3.2 Primary outcome analysis

Primary outcome measures are personality functioning, using the LPFS 2.0 scale, and changes in loneliness, using the Social Isolation Short Form 4a. These measures will be filled out on a weekly basis. The line graphs of the data will be inspected visually first, to see the pattern of observations. We will analyse for trend (progress over time), level of change and stability (variability) within the three phases using within-condition and between-condition visual inspection analyses. The median, median regression, stability envelope of the regression and TAU-U (Parker et al. 2011) will be calculated for each phase, with the median level of change chosen to mitigate the influence of outliers in the data. We will test the hypothesis that the median in the baseline phase exceeds the medians of the treatment and follow-up phase. In addition, non-parametric randomisation tests will be used to statistically evaluate the difference in mean and median scores of the phases statistically. The permutation distance test (Vroegindeweij et al. 2023) will be used since this randomisation test corrects for autocorrelation before the permutation test takes place. In this test a p-value is calculated

for every participant. Moreover, a p-value for the group will also be calculated using the property of p-values that they are uniformly distributed under the null-hypothesis. Using this property, the p-value of the group effect is the probability of a series of individual p-values given the null hypothesis (Onghena et all. 2005). In this test a range of baseline lengths, i.e. the number of baseline measurements, is determined and participants are randomly assigned to one of these baseline lengths. In this test a null distribution of 1000 mean differences is calculated and it is counted how many of the random mean differences is as extreme or more extreme than the observed mean difference (Bouwmeester, 2021).

Service use and self-harm data will be compared between the treatment phases with nonparametric test for repeated measures (Friedman Test), depending on the fulfilment of the requirements for parametric test.

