*ReQol: The Recovering Quality of Life (ReQol-10) scale tracks perceived changes in 'quality of life' over time. This 10-item scale is validated for individuals aged 16 and above. Scores range between 1 and 5, and a shift of 5 points on the scale indicates 'significant improvements' (Keetharuth et al., 2018).

Dialogue: The Dialogue Satisfaction Scale gauges 'patient satisfaction' concerning their quality of life and the treatment they receive. This 11-item scale can be analysed item-wise or by calculating a mean score across all items. In this study, an overall mean score will be used, which ranges from 1 to 7. Scores above 5 suggest high satisfaction, potentially indicating that secondary mental health care might no longer be necessary. Conversely, scores below 4 highlight explicit dissatisfaction, warranting "particular attention" (Mosler et al., 2020).

Columbia Scale: The Columbia Suicidality Response Severity Scale (CSRSS) offers a preliminary indication of an individual's suicide risk. It contains xx items and total or mean scores range from 0 to 1. While it should be used alongside other risk assessment tools, it serves as an initial screening tool for potential suicide risk in adults. The scale has shown sensitivity to changes in suicidality over time (Posner et al., 2011).

Initial screen and evaluation:

Structured Clinical Interview for DSM-5 Personality Disorders

This measure is a validated tool for assessing DSM-5 personality disorders. It has been used with both younger and older adults. There is a procedure for delivering the interview and scoring it. All three members of the team that will deliver this interview have been trained in its use.

Additional processes

To ensure adequate data collection, all outcome measurement forms will be provided to each participant weekly, at their face to face appointment. If the participant does not attend a session, then they will be asked to complete the questionnaire at the next available appointment. Data will be securely stored on a database that will not be accessible by the treatment team, and will only be accessible by the data management and collection team.

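### The protocol credits its analysis with an implicit imputation that none of its listed methods is described as performing, and sections 10.8 and 11.1 give conflicting rules for a missed weekly form

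*Protocol*

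**What the plan says.** Section 10.8 makes two statements about gaps in the data. For random gaps: "In case of random missing data the data analysis contain an implicit imputation". More generally: "In case of missing data we will try to find the reason that the participant did not fill out the questionnaire". It does not say which method does the imputing.

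The methods are listed in section 10.3. For the two weekly primary measures, section 10.3.2 names visual inspection, "The median, median regression, stability envelope of the regression and TAU-U", a permutation distance test on phase mean differences, and a group p-value built from the individual ones. For the three questionnaires, section 10.3.3 names the Friedman test and a Reliable Change Index, with six collection points.

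Two sections say what happens when a session is missed. Section 10.8 has the weekly data gathered "either by the therapist or via phone if the participant is absent". Section 11.1, under additional processes, says: "If the participant does not attend a session, then they will be asked to complete the questionnaire at the next available appointment".

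Section 7.1 allows treatment at home or on a ward in rare cases, "due to frequent treatment disruptions from physical ailments or illnesses in older adults".

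**The concern.** Two things in the text need correcting. First, the protocol asserts a property of its analysis. An analyst or ethics reviewer who reads that sentence will think that missing weeks are dealt with, when the methods as described simply use whatever was observed, and one of them discards participants.

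Second, two members of staff following different sections would build different series from the same participant. One would hold a score for the missed week. The other would hold a score that reflects a later state, with nothing to say whether it is filed under the missed week or the day it was filled in.

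At stake are the estimated change between phases, the spacing of observations on which an autocorrelation correction depends, and the number of participants who enter the questionnaire comparison.

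**Working it through.** **Plan's own figure.** Section 10.1 states power close to 1 for 10 participants and d = 1. A simulation used 8 baseline and 72 treatment weeks (section 16.4), AR(1) errors, thinning to every k-th week, a permutation test on mean differences, and p-values combined by their sum. Not in the protocol and therefore assumed: one-sided 0.05, autocorrelation 0 to 0.5, k = 1 to 3, d in within-person SD. Group power was 0.99 to 1.00, so the stated figure reproduces. Rejection with no effect and nothing missing was 0.02 to 0.07.

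**Do the listed methods impute?**

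| Method | Treatment of a missing week or visit, as described |
|---|---|
| Median, median regression, stability envelope, Tau-U | computed on observed points |
| Permutation distance test | mean difference of observed points; the stated property is autocorrelation correction |
| Combined p-value | takes the individual p-values as given |
| Friedman (standard form) | drops a participant with any missing cell |
| Reliable Change Index | needs both scores of a pair |

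No likelihood-based model or multiple imputation is listed.

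**Friedman, complete rows.** Assume a share q missing at each time point, independent across time points, with all six points in the test. The share of complete rows is (1 − q)^6.
- q = 5%: 0.95^6 = 0.735, which is 7.4 of 10 or 10.3 of 14.
- q = 10%: 0.90^6 = 0.531, which is 5.3 of 10 or 7.4 of 14.

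Section 3.7 lists only five points (0, 6, 12, 18 and 24 months). With five, the shares are 0.95^5 = 0.774 and 0.90^5 = 0.590.

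**The two rules for a missed session.** Under 10.8 the week keeps its own score, taken by phone. Under 11.1 the score is obtained later. Section 11.1 does not say whether that form is dated to the missed week or to the day of completion.

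**Possible bias in the phase contrast.** Let the attended weeks of a phase have mean μ, let a share m be missed, and let missed weeks be δ SD worse (higher).
- True phase mean: (1 − m)μ + m(μ + δ) = μ + mδ.
- Mean with missed weeks omitted: μ, so the error is −mδ.
- Mean with a later attended week's score filed in the gap: expected value again μ, so the error is the same.
- Error in baseline minus treatment: (m_T − m_B)δ, where T is treatment and B is baseline.

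Results:
- m_T = 20%, m_B = 0: δ = 0 gives 0; δ = 0.5 gives 0.2 × 0.5 = 0.10 SD; δ = 1 gives 0.2 × 1 = 0.20 SD.
- m_T = m_B = 20%, δ = 1: (0.2 − 0.2) × 1 = 0.

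In simulation at nominal 20% in treatment only, the error in the treatment mean was −0.002, −0.11 and −0.22 SD when missed weeks were omitted, and +0.001, −0.12 and −0.22 SD when they were filled from the next attended week. The values slightly exceed mδ because whole bouts of up to three weeks overshoot 20%. Medians moved by similar amounts. With equal loss in both phases the simulated bias was about 0.00. Group power at d = 1 stayed at 1.00 throughout.

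**The case against.** The strongest reply has four parts.

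- The quoted sentence covers random gaps only, and for those both omission and later filling leave the mean essentially unbiased. That is correct. It limits the consequence but does not make the sentence true.
- A mean over observed weeks equals the mean after filling each gap with the phase mean, so implicit imputation may be a loose name for available-case analysis. The Single Case Designs app may also treat gaps in a way the documents do not show. Both are possible. If either is meant, the protocol should say so. Neither reading fits the standard Friedman test.
- Detailed missing-data methods are often left to an analysis plan that is not shown. That is fair, and the lack of detail is not the point here. The point is a property that is asserted and two rules that conflict, and both stand in this document.
- A missed session need not be a missed form. Section 4 has forms completed away from the clinic and sent in by envelope, section 10.8 provides for the phone, and section 7.1 mentions illness in order to explain home and ward treatment. This stands, and it is why no missing rate can be inferred.

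A reader might go further and infer that illness weeks will bias the treatment mean and often make the group test falsely significant. The documents do not support that. It needs a missing rate, a score difference and heavier loss in treatment than in baseline, and none of these is given. Heavier loss in treatment is plausible, since section 10.8 ties collection to the individual session and weekly individual appointments start with treatment, but it is not documented.

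**Conclusion.** The point holds in limited form. The imputation sentence in section 10.8 is unsupported by any method as the protocol describes it, and sections 10.8 and 11.1 contradict each other on how a missed primary-outcome form is obtained. Both are errors of statement and need correcting whatever the amount of missing data turns out to be.

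Bias in the phase contrast is a conditional risk. It requires illness weeks that score differently and are lost unequally between phases. The range of 0 to about 0.2 SD, against a planned effect of d = 1, rests wholly on the assumed 20% loss in treatment only and missed weeks 0 to 1 SD worse. The stated group power is not threatened. The loss of rows in the Friedman test depends on assumed rates of 5% to 10% per time point and on independence between them.

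**What to change.** 1. Delete the imputation sentence, or replace it with a statement of what the software does with a missing week.
2. Reconcile sections 10.8 and 11.1 to one rule. Same-week telephone completion is already provided for in 10.8. Record the completion date of every form, and do not count a late form as the missed week.
3. Keep each series on the calendar-week index with missing weeks left missing, so that the distance between observations in the permutation test means weeks.
4. Add a sensitivity analysis that shifts the scores of illness-missed weeks over a stated range in both phases, and one that excludes late forms.
5. Beside the Friedman test, add an analysis of the six-time-point questionnaires that uses incomplete rows, such as a mixed model or a Friedman-type test that allows missing cells.

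The cost is protocol wording, a date field on the form, and a modest amount of extra analysis. A mixed model adds a distributional assumption that 10 to 14 participants can hardly check, and it addresses gaps that are missing at random. It would not by itself remove bias from illness weeks, which is why item 4 is needed. Completion dates should be settled before data collection, since undated forms are hard to repair later.

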10.10 Economic evaluation

Not applicable

11 DATA MANAGEMENT

11.1 Data collection tools and source document identification

Source documents obtained standardised tools

All source documents below are validated tools used to measure outcomes, or to in the use of establishing diagnostic criteria for inclusion.

Primary outcome tools:

Changes in Personality Functioning Using the Level of Personality Functioning Scale Brief Form (LPFS-BF 2.0)

The main objective of this study is to evaluate the change in personality functioning and social isolation in older adults undergoing MBT.

The LPFS 2.0 is a 12-item questionnaire that assesses personality functioning on a 4-point scale (Bender et al., 2011). This tool offers insights into the severity of personality pathology and sheds light on self and interpersonal functioning (Hutsebaut et al., 2016). The LPFS 2.0 has been empirically validated for older adults and has proven valuable in assessing personality functioning in this demographic (Stone et al., 2021).

To ensure adequate statistical power, the LPFS-BF will be administered weekly, following each individual therapy session. This frequent data collection will enhance the reliability of observed changes.

Loneliness Measured by the Social Isolation Short Form 4a

The Social Isolation Short Form 4a, derived from the more extensive UCLA Loneliness Scale, is a globally recognized tool for measuring loneliness. It aligns with the UK's Office for National Statistics recommendations for assessing loneliness (ONS, 2018) and has demonstrated reliability in gauging social isolation. Although a more detailed version, the Social Isolation Short Form 8a, is available and offers increased reliability, its length might be burdensome for weekly assessments. Therefore, this study proposes using the shorter form as a primary outcome. It will be administered weekly too.

Secondary Outcome:

Other Routine Outcome Measures: Quality of Life, Patient Satisfaction, and Suicidality

In addition to the weekly assessments, participants will complete three other questionnaires at start of baseline, start of treatment, 6 months, 12 months, and 18 months into the treatment and at end of follow up. These scales evaluate quality of life (ReQol), patient satisfaction (Dialogue), and suicidality (Columbia Scale).

*ReQol: The Recovering Quality of Life (ReQol-10) scale tracks perceived changes in 'quality of life' over time. This 10-item scale is validated for individuals aged 16 and above. Scores range between 1 and 5, and a shift of 5 points on the scale indicates 'significant improvements' (Keetharuth et al., 2018).

Dialogue: The Dialogue Satisfaction Scale gauges 'patient satisfaction' concerning their quality of life and the treatment they receive. This 11-item scale can be analysed item-wise or by calculating a mean score across all items. In this study, an overall mean score will be used, which ranges from 1 to 7. Scores above 5 suggest high satisfaction, potentially indicating that secondary mental health care might no longer be necessary. Conversely, scores below 4 highlight explicit dissatisfaction, warranting "particular attention" (Mosler et al., 2020).

Columbia Scale: The Columbia Suicidality Response Severity Scale (CSRSS) offers a preliminary indication of an individual's suicide risk. It contains xx items and total or mean scores range from 0 to 1. While it should be used alongside other risk assessment tools, it serves as an initial screening tool for potential suicide risk in adults. The scale has shown sensitivity to changes in suicidality over time (Posner et al., 2011).

Initial screen and evaluation:

Structured Clinical Interview for DSM-5 Personality Disorders

This measure is a validated tool for assessing DSM-5 personality disorders. It has been used with both younger and older adults. There is a procedure for delivering the interview and scoring it. All three members of the team that will deliver this interview have been trained in its use.

Additional processes

To ensure adequate data collection, all outcome measurement forms will be provided to each participant weekly, at their face to face appointment. If the participant does not attend a session, then they will be asked to complete the questionnaire at the next available appointment. Data will be securely stored on a database that will not be accessible by the treatment team, and will only be accessible by the data management and collection team.

11.2 Data handling and record keeping

Four systems will be used to manage data. The PARIS system for clinical data, a secure database for outcome measures, SPSS software to manage statistics, and the Single Case Designs app to managed data relating to SCD portion of the study.

For clinical data, including records of appointments, and clinical communication, this will be recorded on PARIS, which is the local NHS trust's recording software. Standard local processes will be followed, and adhered to.

Outcome data will be securely stored on a database, validated by the research and development team. The SOPs for the use of the system will be followed, and an audit trail of data changes will be maintained to ensure that there is no deletion of entered data. The system will be secure to protect against unauthorized access. Upon the commencement of the trial, a list of the individuals authorized to make data changes will be compiled. They will be responsible for data entry, maintain adequate backups of the data, and safeguarding the blinding of the trial to the clinical team. Source data will be archived. If data are transformed during processing, it should always be possible to compare the original data and observations with the processed data. Participant identification codes will be used to ensure identification of all the data reported for each participant.

11.3 Access to Data

Direct access will be granted to authorised representatives from the Sponsor, host institution and the regulatory authorities to permit trial-related monitoring, audits and inspections- in line with participant consent.

